9.3.2 Exclusion Criteria

Subjects who meet any of the following criteria will be excluded from this study:

1. Females who are breastfeeding or pregnant at Screening or Baseline (as documented by a positive beta-human chorionic gonadotropin test. A separate baseline assessment is required if a negative screening pregnancy test was obtained more than 72 hours before the first dose of study drug. Females of child-bearing potential who:
 - within 28 days before study entry, did not use a highly effective method of contraception, which includes any of the following:
 - total abstinence (if it is their preferred and usual lifestyle)
 - an intrauterine device or intrauterine hormone-releasing system
 - an oral contraceptive (Subject must be on a stable dose of the same oral contraceptive product for at least 28 days before dosing and throughout the study and for 28 days after study drug discontinuation.)
 - have a vasectomized partner with confirmed azoospermia
 - do not agree to use a highly effective method of contraception (as described above) throughout the entire study period and for 28 days after study drug discontinuation.

For sites outside of the European Union, it is permissible that if a highly effective method of contraception is not appropriate or acceptable to the subject, then the subject must agree to use a medically acceptable method of contraception, ie, double-barrier methods of contraception such as condom plus diaphragm or cervical/vault cap with spermicide.

NOTE: All females will be considered to be of child-bearing potential unless they are postmenopausal (amenorrheic for at least 12 consecutive months, in the appropriate age group, and without other known or suspected cause) or have been sterilized surgically

- (ie, bilateral tubal ligation, total hysterectomy, or bilateral oophorectomy, all with surgery at least 1 month before dosing)
2. Any condition that may be contributing to cognitive impairment above and beyond that caused by the subject's AD
 3. Subjects with a history of seizures within 5 years of Screening or subjects with disturbance likely to be due to seizures within 5 years of Screening
 4. History of transient ischemic attacks (TIA) or stroke within 12 months of Screening
 5. Modified Hachinski Ischemia Score greater than 4 at Screening
 6. Any of the following psychiatric symptoms:
 - Psychiatric diagnosis or symptoms, (eg, hallucinations, major depression, or delusions) that, in the opinion of the investigator, could interfere with study procedures
 - Has a "yes" answer to C-SSRS suicidal ideation items 4 or 5, or any suicidal behavior within 6 months before Screening, at Screening, or at the Randomization Visit, or has been hospitalized or treated for suicidal behavior in the past 5 years before Screening
 7. Have any contraindications to MRI scanning, including cardiac pacemaker/defibrillator, ferromagnetic metal implants (eg, in skull and cardiac devices other than those approved as safe for use in MRI scanners) or
 - Have any evidence of other clinically significant lesions that could indicate a dementia diagnosis other than AD on brain MRI at Screening.
 - Exhibit other significant pathological findings on central read of the brain MRI at Screening, including but not limited to: an area of superficial siderosis; evidence of cerebral vasogenic edema; evidence of cerebral contusion, encephalomalacia, aneurysms, vascular malformations, or infective lesions; evidence of multiple infarcts; evidence of stroke involving a major vascular territory; severe small vessel or diffuse white matter disease as defined by a score of 3 on the age-related white matter changes score ([Wahlund, et al., 2001](#)); space occupying lesions; or brain tumors (however, lesions diagnosed as meningiomas or arachnoid cysts and less than 1 cm at their greatest diameter need not be exclusionary). (revised per Amendments 03 and 05).
 8. Subjects who have a history of moderate to severe hepatic impairment (eg, Child-Pugh Class B or C). Any 2 of the following criteria at Screening would exclude the subject: INR ≥ 1.7 ; bilirubin $\geq 1.5 \times$ ULN; albumin $<$ LLN; ascites or hepatic encephalopathy. Please note that a single significant abnormality could meet criteria for moderate impairment. (revised per Amendment 01)
 9. Results of laboratory tests conducted during Screening that are outside the following limits:
 - Absolute lymphocyte count (ALC) below Lower Limit of Normal (LLN) or below 800 per mm^3 (whichever is higher); ALC will be derived from the complete blood count (CBC) with differential representing the normal lymphocytes (with atypical lymphocytes removed and presented as a separate count if they are present) and

- calculated by the white blood cell count × percentage of lymphocytes. (revised per Amendment 01)
- Thyroid stimulating hormone (TSH) above normal range. Other tests of thyroid function with results outside the normal range should only be exclusionary if they are considered clinically significant by the investigator (this applies to all subjects whether or not they are taking thyroid supplements)
 - Abnormally low (below LLN) serum Vitamin B12 levels (if subject is taking Vitamin B12 injections, level should be at or above the LLN). Levels of Vitamin B12 may be confirmed with reflex testing to include methylmalonic acid (MMA) analysis, if available in region. (revised per Amendment 05)
10. Subjects at risk of increased risk of infection, specifically:
- Subjects with chronic viral hepatitis. Subjects with a history of chronic viral hepatitis C may be included if they meet the following requirements:
 - 1) evidence of treatment with direct antiviral combination therapy
 - 2) evidence of sustained virological response at least 12 weeks post-treatmentThe inclusion of subjects with a history of chronic viral hepatitis C must be discussed and agreed with the medical monitor. (revised per Amendment 03)
 - A history of active tuberculosis disease (TB), a history of ophthalmic shingles or a history of ocular herpes simplex virus (HSV) infection (revised per Amendment 03)
 - Any active infection within the last 4 weeks before randomization. For such cases, the timing of randomization can be extended (up to 4 weeks) to allow the infection to resolve
 - Any immunological disease which is not adequately controlled, or which requires treatment with biologic drugs during the study. History of immunoglobulin deficiency or other immunodeficiency disorders (including subjects known to be HIV positive)
11. Have received any live/live attenuated vaccine in the 3 months before randomization
12. Any chronic inflammatory disease that is not adequately controlled or that requires systemic immunosuppressive or immunomodulatory therapy. (revised per Amendment 03)
- NOTE: The following subjects do not need to be excluded:
- Subjects with seasonal or perennial allergic rhinitis, asthma, or chronic obstructive pulmonary disease where the condition is considered to be stable and adequately controlled by inhaled steroids.
 - Hashimoto's thyroiditis but who are stable on thyroid replacement therapy and not on systemic immunosuppressive therapy.
 - Cutaneous manifestations of immunological disease that do not require systemic immunosuppressive therapy or systemic immunomodulatory therapy (ie, topical steroid treatment is permitted)
13. Any other clinically significant abnormalities, such as:

- Physical examination or vital signs at Screening or Baseline that in the opinion of the investigator require further investigation or treatment or may interfere with study procedures or safety. (revised per Amendment 03)
 - Laboratory tests or ECG at Screening that in the opinion of the investigator require further investigation or treatment or may interfere with study procedures or safety. (revised per Amendment 03)
 - Other medical conditions (eg, cardiac, respiratory, gastrointestinal, psychiatric, renal disease) which are not adequately and stably controlled, or which in the opinion of the investigator(s) could affect the subject's safety or interfere with the study assessments (revised per Amendment 01)
 - Illiteracy, or severe visual or hearing impairment that would prevent the subject from performing psychometric tests accurately
14. A prolonged QTcF interval (QTcF greater than 450 ms according to central reading at Screening). (revised per Amendment 03) If the QTcF machine read is greater than 440 ms on the first single 12-lead ECG, 2 additional 12-lead ECGs will be performed 1 minute apart and the mean of the 3 QTcF values will be calculated. (revised per Amendment 05)
15. Malignant neoplasms within 5 years of Screening (except for basal or squamous cell carcinoma in situ of the skin, or localized prostate cancer in male subjects with treatment cycles completed at least 6 months before Screening). Subjects who had malignant neoplasms but who have had at least 5 years of documented uninterrupted remission before Screening need not be excluded.
16. Hypopigmentation conditions (eg, albinism and vitiligo). Hypopigmentation associated with scarring need not be exclusionary
17. Known or suspected history of drug or alcohol abuse or dependence within 2 years before Screening
18. Taking prohibited medications
19. Have participated in a clinical study involving:
- any therapeutic monoclonal antibody, protein derived from a monoclonal antibody, immunoglobulin therapy, or vaccine within 6 months before Screening for whom it cannot be documented that they were randomized only to placebo or never received study drug
 - elenbecestat
 - any new chemical entity or investigational drug for AD with last study drug dose occurring within 6 months before Screening unless it can be documented that the subject received only placebo (revised per Amendment 05)
 - any other investigational medication (unless it can be documented that the subject received only placebo) or device within 8 weeks or 5 half-lives (whichever is longer) before randomization
20. Planned surgery that requires general, spinal or epidural anesthesia that would take place during the study. Planned surgery which requires only local anesthesia and which can be undertaken as day case without inpatient stay postoperatively need not result in exclusion

if in the opinion of the investigator this operation does not interfere with study procedures and subject safety.

9.3.3 Removal of Subjects from Therapy or Assessment

The investigator may withdraw the subject from the study at any time for safety or administrative reasons. The subject may stop study drug or withdraw from the study at any time for any reason.

Absolute lymphocyte count from the hematology and differential panel will be monitored during the study. Absolute lymphocyte count will be derived from the CBC with differential representing the normal lymphocytes (with atypical lymphocytes removed and presented as a separate count if they are present) and calculated by the white blood cell count \times percentage of lymphocytes. Should a subject develop a Grade 2 or greater lymphocytopenia (less than $800/\text{mm}^3$), the ALC test should be repeated as soon as possible with the repeat blood sample drawn no later than 5 calendar days from the date of the original test result. If confirmed, study drug administration should be interrupted for a minimum period of 2 weeks and for a maximum period of 4 weeks. Restart of study drug may take place only when absolute lymphocyte count returns to greater than $800/\text{mm}^3$. Absolute lymphocyte count will be measured 4 weeks after restart of study drug. Subsequent measurements of ALC will follow the schedule of assessments (Table 5) and any results showing a Grade 2 or greater lymphocytopenia (less than $800/\text{mm}^3$) should be handled as above. If a Grade 2 or greater lymphocytopenia (less than $800/\text{mm}^3$), that is confirmed on repeat testing, occurs twice within a 6 month period, during the Core Study Treatment Period, then the subject should be discontinued permanently from the study drug. In the Extension Phase, if a confirmed Grade 2 or greater lymphocytopenia (less than $800/\text{mm}^3$) occurs twice from Visit 16 onwards during a 6-month period then the subject should also be discontinued permanently from study drug (revised per Amendments 01, 03, and 05).

Subjects who develop moderate or severe hepatic impairment (eg, Child-Pugh Class B or C) during the study must discontinue study drug. (revised per Amendments 01 and 02) Moderate or severe hepatic impairment are defined as any 2 of the following criteria: INR ≥ 1.7 ; bilirubin $\geq 1.5 \times \text{ULN}$; albumin $< \text{LLN}$; ascites or hepatic encephalopathy. Please note that a single significant abnormality could meet criteria for moderate impairment. (revised per Amendment 02)

Subjects who develop seizures will be discontinued from study drug. (revised per Amendment 02)

In the event that a subject develops a severe infection, study drug administration should be interrupted for a maximum period of 4 weeks. Examples of severe infections include the following: sepsis; deep tissue (invasive) infection; any infection requiring IV antibiotics; any infection requiring hospitalization (if outpatient at onset); any infection leading to need for oxygen, pressors or fluids to support blood pressure, or intubation; any infection that requires major surgical intervention; pseudomembranous colitis due to *C. difficile*; typhlitis; osteomyelitis; and meningitis. Subjects who recover from severe infections within 4 weeks may resume treatment if deemed appropriate by the investigator after consultation with the

medical monitor. Subjects should permanently discontinue study drug if the severe infection has not resolved within 4 weeks. (revised per Amendment 02)

As described under Dermatologic Assessment in [Section 9.5.1.5.5](#), in the event that a subject develops any skin rash of moderate to severe intensity, or any rash lasting more than 72 hours regardless of severity (with the exception of oral or genital herpes as described in the next paragraph), study drug administration should be interrupted for a maximum period of 4 weeks and a dermatologic consult will be requested regardless of whether the rash is considered drug related or due to other causes. For cases where the investigator suspects a drug rash, regardless of severity, the subject will be discontinued from study drug, a dermatologic consult will be requested, and a skin biopsy will be performed to confirm the diagnosis. The skin rash will be treated as per standard care and will be followed up until resolution regardless of etiology or severity. Subjects who recover from skin rash within 4 weeks may resume treatment if in the opinion of the dermatologic consult, the rash was not drug related and it is deemed appropriate by the investigator after consultation with the medical monitor. Subjects should permanently discontinue study drug if the skin rash has not resolved within 4 weeks or returns during rechallenge. (revised per Amendment 02)

In the event that a subject develops moderate to severe oral or genital herpes, study drug administration should be interrupted for a maximum period of 4 weeks. Subjects who develop a mild case of oral or genital herpes may remain on study drug even if the event lasts more than 72 hours. Subjects who recover from moderate to severe oral or genital herpes within 4 weeks may resume treatment if it is deemed appropriate by the investigator after consultation with the medical monitor. Subjects should permanently discontinue study drug if the oral or genital herpes has not resolved within 4 weeks or returns during rechallenge. (revised per Amendment 02)

Subjects who discontinue study drug early must complete the ED Visit (within 7 days of the last dose of study drug) and the Follow-up Visits (1 and 3 months after the last dose of study drug). These Follow-up Visits will be conducted to monitor efficacy and safety parameters after early withdrawal from the study or discontinuation of study drug.

For subjects who temporarily suspend study drug (eg, ALC $<800/\text{mm}^3$) but progress to permanently discontinue study drug, the ED and Follow-up Visits should be scheduled as follows: (revised per Amendment 05)

- If ≥ 3 weeks since the last study dose, then the ED Visit should be scheduled immediately, and the 1-month Follow-up Visit will not be required
- If <3 weeks since the last study dose, then the ED visit should be scheduled immediately, and Follow-up Visits at 1 and 3 months after the last dose will be required

All subjects in the Core Study who discontinue study drug before reaching 12 months of treatment will also be asked to return to the clinic for a 12-month clinical assessment and then again at 24 months. Subjects who discontinue treatment between 12 and 24 months of treatment will be asked to return to the clinic for a 24-month clinical assessment. Subjects who discontinue early from study drug are considered “on study” as long as they continue to

return for their regularly scheduled clinical assessments at 12 and 24 months as outlined above, at which efficacy and quality of life will be assessed along with concomitant medications. New AEs will be collected for 4 weeks post last dose and followed up for 12 weeks, or until resolution, whichever comes first. AEs relating to study procedures will be collected until the end of study participation. (revised per Amendment 05) However, subjects who discontinue study drug early are not considered to have ‘completed’ the study as a final Subject Disposition.

The primary reason for discontinuation and all other reason(s) contributing to the subject’s discontinuation from study drug(s) should be collected on the ED from study drug eCRF page. In addition, the date of last dose of study drug(s) will be recorded on the Study Drug Dosing eCRF page. If a subject discontinues study treatment and the study at the same time, the end-of-study procedures (Final Visit) will be followed (see [Section 9.5.5](#)).

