9.1.2.2 Follow-Up Period

All subjects, regardless of whether they complete all 24 months of treatment or discontinue study drug prematurely, will complete 2 post-treatment Follow-up Visits; one 4 weeks after the last dose of study drug and a second 12 weeks after the last dose of study drug (Visit 14 and Visit 15 respectively). If clinically indicated, more frequent safety assessments can be made as UNS assessments or visits during the post-treatment Follow-up Period.

In some cases, UNS visits will be needed to follow up on safety or other findings, and the related assessments (outlined in the Schedule of Assessments) will depend on the reason for the UNS visit, and will be decided at the discretion of the investigator.

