All AEs must be followed for 12 weeks after the subject's last dose, or until resolution, whichever comes first. Subjects who have a Grade 2 or greater lymphocytopenia (less than 800/mm³) during the Follow-up Period (ie, at either Visit 14 or Visit 15) should have ALC measured every 4 weeks until resolution or confirmation of a non drug-related cause of the lymphocytopenia. ALC will be derived from the CBC with differential representing the normal lymphocytes (with atypical lymphocytes removed and presented as a separate count if they are present) and calculated by the white blood cell count × percentage of lymphocytes. (revised per Amendment 01) All SAEs must be followed to resolution or, if resolution is unlikely, to stabilization.

Every effort must be made by the investigator to categorize each AE according to its severity and its relationship to the study treatment.

Assessing Severity of AEs

AEs will be graded on a 3-point scale (mild, moderate, severe) and reported in the detail indicated on the eCRF. The definitions are as follows:

Mild	Discomfort noticed, but no disruption of normal daily activity
Moderate	Discomfort sufficient to reduce or affect normal daily activity
Severe	Incapacitating, with inability to work or to perform normal daily activity

The criteria for assessing severity are different than those used for seriousness (see [Section 9.5.1.5.2](#) for the definition of an SAE).

Assessing Relationship to Study Treatment

Items to be considered when assessing the relationship of an AE to the study treatment are:

- Temporal relationship of the onset of the event to the initiation of the study treatment
- The course of the event, especially the effect of discontinuation of study treatment or reintroduction of study treatment, as applicable
- Whether the event is known to be associated with the study treatment or with other similar treatments
- The presence of risk factors in the study subject known to increase the occurrence of the event
- The presence of nonstudy, treatment-related factors that are known to be associated with the occurrence of the event

Classification of Causality

The relationship of each AE to the study drug will be recorded on the eCRF in response to the following question:

Is there a reasonable possibility that the study drug caused the AE?

Yes (related) A causal relationship between the study drug and the AE is a reasonable possibility.

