Blood samples for clinical chemistry, hematology, and coagulation (revised per Amendment 02)	X	X	X	X	X	X	X	X	X	X	X	X	X	X	X	X	
Urine sample for dipstick urinalysis ^j	X	X	X	X	X	X	X	X	X	X	X	X	X	X	X ^c	X	
Blood sample for immunological assessments, (revised per Amendment 02) ^{ee}	X	X	X	X	X	X	X	X									
PBMCs for storage and testing required (revised per Amendment 05)	X					X		X				X	X				
Urine pregnancy test (females of CBP only) ^k	X		X	X	X	X	X	X	X	X	X	X	X	X	X ^{dd}	X	

Table 5 Schedule of Procedures/Assessments in Study E2609-G000-302 (Revised per Amendments 04 and 05)

Phase Period	Randomization														ED ^b	Follow-Up		UNS Visit ^d
	Treatment												14 ^c	15 ^c				
Visit ^a	2	3	4	5	6	7	8	9	10	11	12	13						
Day	1	15	29	57	85	183	274	365	456	547	638	729			757	813		
Week	1	3	5	9	13	27	40	53	66	79	92	105			109	117		
Weeks elapsed since 1st dose	0	2	4	8	12	26	39	52	65	78	91	104			108	116		
Nominal months elapsed since 1st dose	0		1	2	3	6	9	12	15	18	21	24			25	27		
Procedures/ Assessments																		
Blood sample for viral characterization ^l	X																	
Blood sample for storage for immune status ^m	X		X		X	X		X				X	X	X	X	X	X	
MMSE ⁿ	X					X		X		X		X	X	X	X	X		
CDR ⁿ	X				X	X	X	X	X	X	X	X	X	X	X	X		
ADAS-cog14 ⁿ	X					X		X		X		X	X	X	X	X		
FAQ ⁿ	X					X		X		X		X	X	X	X	X		
Disease Staging ^o					X	X	X	X	X	X	X	X	X			X		
NPI-10	X					X		X		X		X	X			X ^{hh}		
C-SSRS	X	X ^{gg}	X ^{gg}	X ^{gg}	X ^{gg}	X ^{gg}	X ^{gg}	X ^{gg}	X ^{gg}	X ^{gg}	X ^{gg}	X ^{gg}	X	X		X ^{dd}		
Clinical assessment of suicidal thinking and behavior ^p		X	X	X	X	X	X	X	X	X	X			X	X ⁱⁱ	X		
EQ-5D ^q						X		X		X		X	X					
QOL-AD ^r						X		X		X		X	X					
Zarit's Burden Interview of study partner						X		X		X		X	X					
MRI including vMRI and fMRI ^s								X				X	X					
Amyloid PET (optional substudy) ^t								X				X	X			X ^{cc}		
Tau PET (optional substudy) ^u												X	X			X ^{cc}		

Table 5 Schedule of Procedures/Assessments in Study E2609-G000-302 (Revised per Amendments 04 and 05)

Phase Period	Randomization															
	Treatment												Follow-Up		UNS Visit ^d	
Visit ^a	2	3	4	5	6	7	8	9	10	11	12	13	ED ^b	14 ^c		15 ^c
Day	1	15	29	57	85	183	274	365	456	547	638	729		757	813	
Week	1	3	5	9	13	27	40	53	66	79	92	105		109	117	
Weeks elapsed since 1st dose	0	2	4	8	12	26	39	52	65	78	91	104		108	116	
Nominal months elapsed since 1st dose	0		1	2	3	6	9	12	15	18	21	24		25	27	
Procedures/ Assessments																
Telephone contact ^v		X	X		X	X		X		X		X	X			

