Blood samples for PK ^w		X	X		X	X		X		X		X	X			
Blood samples for PD and exploratory biomarkers ^x	X	X	X		X	X		X		X		X	X	X	X	
CSF sampling for PK and PD (optional substudy) ^y												X	X		X ^{cc}	
Adverse events ^{ff}	X	X	X	X	X	X	X	X	X	X	X	X	X	X	X	X
Sleep/Dream Questionnaire ^z	X	X	X	X	X	X	X	X	X	X	X	X	X	X	X	X
Possible Drug Abuse Potential Form/ Questionnaire ^{aa}	X	X	X	X	X	X	X	X	X	X	X	X	X	X	X	X
Randomization	X															
Dispense study drug	X ^{bb}	X	X	X	X	X	X	X	X	X	X					X ^{dd}

Notes

ADAS-cog14 = Alzheimer’s Disease Assessment Scale - Cognitive subscale (14 items), AE = adverse event, CBP = child-bearing potential, CDR = Clinical Dementia Rating scale, CMV = cytomegalovirus, CNS = central nervous system, CSF = cerebrospinal fluid, C-SSRS = Columbia Suicide Severity Rating Scale, ECG = electrocardiogram, ED = Early Discontinuation, EQ-5D = EuroQol-5 Dimensions, FAQ = Functional Assessment Questionnaire (also known as the Functional Activities Questionnaire), fMRI = functional MRI (to be performed task free at resting state), HSV1 = herpes simplex virus 1 (orolabial herpes), HSV2 = herpes simplex virus 2 (genital herpes), INR = International Normalized Ratio, LP = lumbar puncture, MMSE = Mini Mental State Examination, MRI = magnetic resonance imaging, NPI = Neuropsychiatric Inventory, PBMC = peripheral blood mononuclear cell, PD = pharmacodynamics, PET = positron emission tomography, PK = pharmacokinetics, QOL-AD = Quality of Life in Alzheimer’s Disease, QTcF = QTc interval calculated using Fridericia’s formula, UNS = unscheduled, vMRI = volumetric MRI.

a: A window of ±3 days will be permitted for Visits 3 and 4. A window of ±7 days will be permitted for Visits 5 and 6. A window of ±10 days will be permitted for Visits 7 to 13 inclusive (including for subjects who discontinue study drug early but who return for clinical assessments at 12 and 24 months). These windows should be calculated from Day 1. A window of ±3 days calculated from the last dose will be permitted for the Follow-up Visits. If use is made of the permitted visit windows, every effort should be made to bring the subject back in line with the “weeks elapsed since 1st dose” at subsequent visits.

Table 5 Schedule of Procedures/Assessments in Study E2609-G000-302 (Revised per Amendments 04 and 05)

Phase Period	Randomization															
	Treatment												ED ^b	Follow-Up		
Visit ^a	2	3	4	5	6	7	8	9	10	11	12	13	ED ^b	14 ^c	15 ^c	UNS Visit ^d

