Day	1	15	29	57	85	183	274	365	456	547	638	729		757	813	
Week	1	3	5	9	13	27	40	53	66	79	92	105		109	117	
Weeks elapsed since 1st dose	0	2	4	8	12	26	39	52	65	78	91	104		108	116	
Nominal months elapsed since 1st dose	0		1	2	3	6	9	12	15	18	21	24		25	27	
Procedures/ Assessments																

- b: Subjects who discontinue taking study drug prematurely for any reason will undergo an ED Visit within 7 days of their last dose of study drug. In addition, Follow-up Visits will be scheduled 4 and 12 weeks after the last dose of study drug (Visit 14 and Visit 15, respectively). Subjects who discontinue study drug before reaching 12 months of treatment will also be asked to return to the clinic for a 12 month clinical assessment and then again at 24 months. Subjects who discontinue treatment between 12 and 24 months of treatment will be asked to return to the clinic for a 24 month clinical assessment. Subjects who discontinue early from study drug are considered “on study” as long as they continue to return for their clinical assessments at 12 and 24 months as outlined above, at which efficacy (MMSE, CDR, ADAS- cog14) and quality of life (EQ-5D, QOL-AD and Zarit’s Burden Interview) will be assessed along with concomitant medications. New AEs will be collected for 4 weeks post last dose and followed-up for 12 weeks, or until resolution, whichever comes first. If >4 weeks post last dose only AEs relating to study procedures will be collected. These 12 and 24 month clinical assessment visits do not need to be attended if they fall within 8 days (visit window) after the ED Visit or within ±8 days of either of the Follow-up Visits (Visit 14 and Visit 15).

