9.5.2.2 Description of Procedures/Assessments Schedule

Please refer to [Table 4](#) and [Table 5](#) for the timings of the procedures and assessments to be performed during the study. Screening assessments will be organized into 5 tiers (see [Table 4](#)). See [Section 9.5.1](#) for a full description of the procedures and assessments to be performed during this study.

[Table 6](#) presents the number of blood and CSF samples, and the estimated total volume of blood and CSF that will be collected throughout the study. (revised per Amendment 02) Additional samples may be taken at the discretion of the investigator if the results of any tests fall outside reference ranges or if clinical symptoms necessitate testing to ensure subject safety. Actual specimen volumes may vary based on local regulations. (revised per Amendment 02)

Table 6 Summary of Estimated Blood and CSF Sample Volumes

Assessment	Total Number of Collection Time Points	Sample Volume, Number of Time Points × Volume per Collection (mL)			Total Volume ^a (mL)
		Screening Visits	Visit 2 Baseline (predose) (revised per Amendment 03)	Treatment and Follow-Up Periods	
Blood					
Clinical chemistry (revised per Amendments 02 and 03)	15	1×2.5 mL	1×2.5 mL	13×2.5 mL	37.5 mL
Serum pregnancy test at Screening (females of child-bearing potential only)	0	can use blood drawn for clinical chemistry	can use blood drawn for clinical chemistry	none	no additional volume
Hematology (revised per Amendment 03)	15	1×2 mL	1×2 mL	13×2 mL	30 mL
Coagulation (revised per Amendments 02 and 03)	15	1×1.8 mL	1×1.8 mL	13×1.8 mL	27 mL
Thyroid function tests (thyroid stimulating hormone, free triiodothyronine and free thyroxine)	1	1×5 mL	none	none	5 mL
Viral screen at Screening (Hepatitis B and C) (revised per Amendment 02)	1	1×2.5 mL	none	none	2.5 mL
Viral characterization at Visit 2 (previous exposure to CMV, HSV1, HSV2, etc.) (revised per Amendments 02 and 03)	1	none	1×3.5 mL	none	3.5 mL

Table 6 Summary of Estimated Blood and CSF Sample Volumes

Assessment	Total Number of Collection Time Points	Sample Volume, Number of Time Points × Volume per Collection (mL)			Total Volume ^a (mL)
		Screening Visits	Visit 2 Baseline (predose) (revised per Amendment 03)	Treatment and Follow-Up Periods	
Vitamin B12 at Screening and MMA where available (revised per Amendments 02, 03, and 05)	0	can use blood drawn for TFT	none	none	no additional volume

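### A low lymphocyte count at the Early Discontinuation Visit that replaces Visit 14 does not start the 4-weekly ALC rule, so the next fixed count is Visit 15

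*Protocol*

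**What the plan says.** **Suspension and restart (Section 9.3.3).** A confirmed ALC below 800/mm³ interrupts study drug for 2 to 4 weeks. Dosing may resume only once the count is back above 800/mm³.

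**When a suspension becomes permanent (same section, Amendment 05).** At 3 weeks or more since the last dose, "then the ED Visit should be scheduled immediately, and the 1-month Follow-up Visit will not be required". Below 3 weeks, the ED Visit and both Follow-up Visits stand.

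**Off-drug lymphocyte monitoring (Section 9.5.1.5.1, repeated in Table 5 footnote c).** Subjects with Grade 2 or greater lymphocytopenia "during the Follow-up Period (ie, at either Visit 14 or Visit 15) should have ALC measured every 4 weeks until resolution", or until a cause other than the drug is confirmed. The ED Visit is not named in either place.

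**Scheduled samples (Table 5).** The row "Blood samples for clinical chemistry, hematology, and coagulation" is marked at the ED Visit, Visit 14, Visit 15 and unscheduled visits. The ED Visit therefore does yield an ALC.

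**General follow-up wording.** Section 9.1.2.2 says that all subjects "will complete 2 post-treatment Follow-up Visits; one 4 weeks after the last dose of study drug", with a second visit at 12 weeks. Table 5 footnote b and Section 9.5.5 say of early discontinuers that "Follow-up Visits will be scheduled 4 and 12 weeks after the last dose of study drug", and Table 5 footnote c also gives every subject both visits. None of these carries an exception for the Section 9.3.3 waiver.

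**The concern.** The waiver is sensible in itself: an ED Visit held 3 to 4 weeks after the last dose falls on or near the date of Visit 14, and two visits there would be redundant. The difficulty is that the ED Visit takes over Visit 14's place in the calendar without its function as a trigger. The same low count on day 28 leads to 4-weekly testing if the visit is labelled Visit 14, and to no fixed retest before day 84 if it is labelled ED. The documents give no reason for treating the two differently.

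The path leads to the subjects for whom off-drug monitoring is most relevant. Restart needs a count above 800/mm³ and the suspension is capped at 4 weeks, so a subject still low at 4 weeks cannot resume and has already passed the 3-week threshold. What is at stake is a safety interval that the protocol sets for itself, and consistency between sites, since the general wording and the waiver give two readings of whether Visit 14 takes place.

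**Working it through.** The plan states no figure for this gap. It follows from the visit schedule.

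**Inputs**
- Visits 14 and 15: 4 and 12 weeks after the last dose (Section 9.1.2.2). Check against the Table 5 day row: 757 − 729 = 28 days and 813 − 729 = 84 days, which agree.
- Window: "A window of ±3 days calculated from the last dose will be permitted for the Follow-up Visits" (Table 5 footnote a), so Visit 15 falls on day 81 to 87.
- ED Visit: day 21 (the waiver begins at 3 weeks) to day 28 (the suspension is capped at 4 weeks), Section 9.3.3.
- Retest interval under the rule: 28 days.

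**Gap = day of Visit 15 − day of ED Visit**

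| ED Visit | Gap to day 84 | With window (day 81 to 87) | Under the 4-weekly rule |
|---|---|---|---|
| Day 28 | 84 − 28 = 56 days | 53 to 59 days | 28 days |
| Day 21 | 84 − 21 = 63 days | 60 to 66 days | 28 days |

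The range is 56 to 63 days, or 53 to 66 with the window.

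**Counts missed**
- ED on day 28: the rule would give counts on days 28, 56 and 84; the plan as written gives days 28 and 84. One is missed, at day 56.
- ED on day 21: the rule would give days 21, 49 and 77; the plan gives days 21 and 84. The day-49 count is missed. The day-77 count falls 7 days before Visit 15, so Visit 15 largely covers it.

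**Does any other text fill the interval?**
- *Repeat within 5 days (Section 9.3.3).* Later low results from Table 5 draws are to be handled in the same way as the first. That sentence comes after the restart step, and the handling it refers to is confirming a count and interrupting dosing. Whether it reaches a subject already off drug is arguable. If it does, it adds one confirmatory count and no recurring interval.
- *Adverse event follow-up (Section 9.5.1.5.1).* A laboratory abnormality that leads to withholding or withdrawal of drug is an adverse event, and adverse events must be followed for 12 weeks after the last dose or until resolution. This is mandatory but sets no ALC interval.
- *Discretionary testing.* Section 9.1.2.2 allows unscheduled assessments, and Section 9.5.2.2 says "Additional samples may be taken at the discretion of the investigator if the results of any tests fall outside reference ranges". Both permit testing; neither requires it.
- *Return assessments at 12 and 24 months (Section 9.3.3, Table 5 footnote b).* These list efficacy, quality of life and concomitant medications, not hematology.
- *General Visit 14 wording (Sections 9.1.2.2 and 9.5.5, Table 5 footnotes b and c).* Read alone, it would keep Visit 14 and close the gap. It conflicts with the more specific waiver and does not override it.

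**The case against.** A reader might infer that a low count at this ED Visit starts nothing. The documents do not support that. The 5-day repeat arguably applies, and a low count that led to suspension is an adverse event by definition, with mandatory follow-up. Section 9.5.1.5.1 also requires significant laboratory abnormalities emerging on treatment to be described to the medical monitor, with outcome. What is absent is a stated retest interval.

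A reader might also infer that off-drug monitoring is lost on this path. It is not: Visit 15 is still required, and a low count there starts the 4-weekly rule.

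The path is narrow. The only explicit ALC rule for permanent discontinuation is a second confirmed low count within 6 months; if such subjects are stopped on confirmation they will ordinarily be less than 3 weeks from the last dose and keep both Follow-up Visits. Section 7.1 reports lymphocyte effects in the multiple-dose study resolving between 6 and 21 days after the last dose, so a count still low at 3 to 4 weeks should be uncommon. That recovery followed 14 days of dosing, whereas this study doses for up to 24 months, so the reassurance is partial. The infection concern in Section 7.1 is tied to 200 and 400 mg; at 50 to 100 mg it reports only some reduction in CD4 counts.

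Finally, a visit that is not required is still permitted, and a site following the general wording would hold it. That depends on which section the site reads first.

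These points limit the size of the matter. None of them supplies a recurring interval between the ED Visit and Visit 15.

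**Conclusion.** The point holds as a minor one. Where a suspension becomes permanent at 3 weeks or more, a count still low at the ED Visit has no required 4-weekly retest for 56 to 63 days (53 to 66 with the window), against 28 days under the protocol's own rule. About one scheduled count is missed and monitoring is delayed.

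This assumes that the ED Visit falls on day 21 to 28 after the last dose, that the Amendment 05 waiver prevails over the general Visit 14 wording because it is more specific, and that the visits listed in the 4-weekly rule are exhaustive, as its wording indicates. The documents give no incidence, so the number of affected subjects cannot be calculated; the recovery times in Section 7.1 suggest that it is small. There is no basis for inferring an effect on the primary CDR-SB analysis, or a demonstrated infection risk at 50 mg.

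**What to change.** In Section 9.5.1.5.1 and Table 5 footnote c, widen the trigger to: *at the ED Visit when the 1-month Follow-up Visit is waived under Section 9.3.3, at Visit 14, or at Visit 15*. In Sections 9.1.2.2 and 9.5.5 and in Table 5 footnotes b and c, add: *except where Section 9.3.3 waives Visit 14*.

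The public file contains these sections twice. The second copy lacks the Amendment 06 text in Section 5.3 and so appears to be the earlier version; it needs the same change only if it is still current.

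With the fix, the longest interval between required counts while the count stays low is 28 days. The cost is a few phrases in the next amendment and, per affected subject, about one extra hematology sample (2 mL, Table 6) with the attendance for it. With an ED Visit on day 21, a second extra sample at day 77 arises only if it is not combined with Visit 15.
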